5.6.2.7. Follow-Up Adjusted Subject Incidence Rate per 100 Subject Years: Mortality

Deaths will be assigned to a timepoint (i.e. Week 52, Year 2, Year 3, Year 4 or Year 5) using the survival status nominal visit where the death was reported. Cumulative deaths to each timepoint will be summarized and follow-up adjusted subject incidence rates calculated.

The follow-up adjusted subject incidence rate presented for each timepoint will be a cumulative follow-up adjusted subject incidence rate from study treatment start date to the appropriate follow-up period. The subject years will be the sum of subject years for all subjects to that timepoint (as described in Section 5.6.2.6).

$$\text{Incidence Rate} = 100 \times \frac{\text{Number of subjects with an event}}{\text{Subject Years}}$$

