5.6.2.3. Year Intervals

All-cause mortality and malignancies (including NMSC) will be summarized by follow-up year. The nominal visit will be used for yearly summaries. There will be no slotting of visits into years using dates.

The planned study day of each year is as follows (using a 365-day calendar year):

Study Year	Planned Study Day of Visit
Week 52	Day 365 ± 7
Year 2 Follow-Up	Day 730 ± 30
Year 3 Follow-Up	Day 1095 ± 30
Year 4 Follow-Up	Day 1460 ± 30
Year 5 Follow-Up	Day 1825 ± 30

Note: Treatment start date is Day 1.

Note: The protocol study calendar refers to Week 52 as Day 364 (and uses Day 0 terminology). This equates to study Day 365, as calculation of study day does not allow a Day 0 but starts at Day 1.

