5.6.2.6. Subjects Years Follow-Up: Mortality

Subject years follow-up for mortality is calculated as described below, regardless of the primary cause of death (COVID-19 or other).

In order to calculate the follow-up adjusted incidence rate of mortality per 100 subject years by follow-up year (cumulative), the subject years follow up will need to be defined for each subject at each follow-up time point.

For each subject a single date of death or last known alive date will be derived as follows.

For subjects who entered the follow-up period (i.e. are in any of the Year 2 to 5 population subsets):

- For subjects who have died, the date of death will be used in the subject follow-up years calculations.
- For subjects who have not died, the latest last known alive date across all follow-up visits will be found.

For subjects who did not enter the follow-up period (i.e. are not in any of the Year 2 to 5 population subsets):

- For subjects who have died, the date of death will be used in the subject follow-up years calculations.
- For subjects who were alive or lost to follow-up at the Week 52 survival status assessment, the last known alive date from the Week 52 survival status form will be used. In calculations, the data for these subjects will be truncated so that subject follow-up years does not exceed 365 days for these subjects.
- For subjects where the Week 52 survival status was missing, the study withdrawal or completion date (DSSTDT) will be used as the last known alive date. In calculations, the data for these subjects will be truncated so that subject follow-up years does not exceed 365 days for these subjects. Note: there were four subjects with missing Week 52 survival status where the study withdrawal or completion date was missing; for these subjects the study agent discontinuation date (IPDISCDT) was used as the last known alive date.

Using this date of death or last known alive date, the total subject follow-up will be derived for each subject as:

- Subject follow-up (days) = (Date of death/Last Known Alive Date – Study Treatment Start Date +1)

The amount of subject follow-up days contributing to each of the cumulative timepoints (by Week 52, by Year 2 follow-up, by Year 3 follow-up, by Year 4 follow-up, by Year 5 follow-up) is described below. In order to account for date of death or last known alive date which is out of the correct range of study days for a particular year, the following derivation will be used:

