Study Year	Subject Follow-Up (days)
By Week 52	Minimum (Date of death/Last Known Alive Date – Treatment Start Date + 1, 365)
By Year 2 Follow-Up	Minimum (Date of death/Last Known Alive Date – Treatment Start Date + 1, 730)
By Year 3 Follow-Up	Minimum (Date of death/Last Known Alive Date – Treatment Start Date + 1, 1095)
By Year 4 Follow-Up	Minimum (Date of death/Last Known Alive Date – Treatment Start Date + 1, 1460)

Study Year	Subject Follow-Up (days)
By Year 5 Follow-Up	Minimum (Date of death/Last Known Alive Date – Treatment Start Date + 1, 1825)

Note: individual subjects will only be allowed to contribute a maximum of 365 days for each individual follow-up year, regardless of when the follow-up visit was performed.

Note: For each subject, subject follow-up for each time period is cumulative since study treatment start date. For example, 'by Year 2 follow-up' includes follow-up time during Year 1 and follow-up time during Year 2 (to a maximum of 730 days).

The subject follow-up days will be converted to years as follows:

- Subject follow-up (years) = subject follow-up (days) / 365.25

The total follow-up years will be calculated for each of the timepoints as the sum of the subject follow-up years for that timepoint for all subjects in the As-Treated population.

An example of the amount of subject follow-up days included in each year period, for subjects where the date of death or the last known alive date falls within the correct study day range for each year, is:

Subjects Enter Follow-Up Period [1]	Subject Years Follow-Up Included By Year	Subjects Years Follow-Up (days)
Subject death during Year 2 Follow-Up	Week 52	365
	Year 2 Follow-Up	Date of death – Treatment Start Date +1
	Year 3 Follow-Up	Date of death – Treatment Start Date +1
	Year 4 Follow-Up	Date of death – Treatment Start Date +1
	Year 5 Follow-Up	Date of death – Treatment Start Date +1
Subject death during Year 3 Follow-Up	Week 52	365
	Year 2 Follow-Up	730
	Year 3 Follow-Up	Date of death – Treatment Start Date +1
	Year 4 Follow-Up	Date of death – Treatment Start Date +1
	Year 5 Follow-Up	Date of death – Treatment Start Date +1
Subject death during Year 4 Follow-Up	Week 52	365
	Year 2 Follow-Up	730
	Year 3 Follow-Up	1095
	Year 4 Follow-Up	Date of death – Treatment Start Date +1
	Year 5 Follow-Up	Date of death – Treatment Start Date +1
Subject death during Year 5 Follow-Up	Week 52	365
	Year 2 Follow-Up	730
	Year 3 Follow-Up	1095
	Year 4 Follow-Up	1460

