	Year 5 Follow-Up	Date of death – Treatment Start Date +1
Subject Last Known to be Alive during Year 2 Follow-Up	Week 52	365
	Year 2 Follow-Up	Last known alive date – Treatment Start Date +1
	Year 3 Follow-Up	Last known alive date – Treatment Start Date +1
	Year 4 Follow-Up	Last known alive date – Treatment Start Date +1
	Year 5 Follow-Up	Last known alive date – Treatment Start Date +1
Subject Last Known to be Alive during	Week 52	365
	Year 2 Follow-Up	730

Subjects Enter Follow-Up Period [1]	Subject Years Follow-Up Included By Year	Subjects Years Follow-Up (days)
Year 3 Follow-Up	Year 3 Follow-Up	Last known alive date – Treatment Start Date +1
	Year 4 Follow-Up	Last known alive date – Treatment Start Date +1
	Year 5 Follow-Up	Last known alive date – Treatment Start Date +1
Subject Last Known to be Alive during Year 4 Follow-Up	Week 52	365
	Year 2 Follow-Up	730
	Year 3 Follow-Up	1095
	Year 4 Follow-Up	Last known alive date – Treatment Start Date +1
	Year 5 Follow-Up	Last known alive date – Treatment Start Date +1
Subject Last Known to be Alive during Year 5 Follow-Up	Week 52	365
	Year 2 Follow-Up	730
	Year 3 Follow-Up	1095
	Year 4 Follow-Up	1460
	Year 5 Follow-Up	Last known alive date – Treatment Start Date +1

[1] Based on As-Treated Population Subsets for Years 2 to 5 Follow-Up.

Subjects Do Not Enter Follow-Up Period [1]	Subject Years Follow-Up Included By Year	Subjects Years Follow-Up (days)
Subject death during Week 52	Week 52	Date of death – Treatment Start Date +1
	Year 2 Follow-Up	Date of death – Treatment Start Date +1
	Year 3 Follow-Up	Date of death – Treatment Start Date +1
	Year 4 Follow-Up	Date of death – Treatment Start Date +1
	Year 5 Follow-Up	Date of death – Treatment Start Date +1
Subject Last Known to be Alive during Week 52	Week 52	Minimum (Last known alive date – Treatment Start Date +1, 365)
	Year 2 Follow-Up	Minimum (Last known alive date – Treatment Start Date +1, 365)
	Year 3 Follow-Up	Minimum (Last known alive date – Treatment Start Date +1, 365)
	Year 4 Follow-Up	Minimum (Last known alive date – Treatment Start Date +1, 365)
	Year 5 Follow-Up	Minimum (Last known alive date – Treatment Start Date +1, 365)

[1] Based on As-Treated Population Subsets for Years 2 to 5 Follow-Up.

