5.6.2.9. Subject Years Follow-Up: Malignancy Event Rate

In order to calculate the follow-up adjusted event rate of new malignancies per 100 subject years by follow-up year (cumulative), the subject years follow up will need to be defined for each subject at each follow-up time point.

As subjects can report more than one new malignancy, and this is an event level calculation, subject follow-up years will not be truncated at the date of first diagnosis for subjects reporting a new malignancy.

For each subject a single date of last follow-up contact date will be derived as follows.

For subjects who entered the follow-up period (i.e. are in any of the Year 2 to 5 population subsets):

- The date of last follow-up contact across all follow-up visits will be found (using all visits where the new malignancy question was answered as NO or YES) and used as the censoring date. If this follow-up contact date is later than the last known alive date (or date of death) used in the mortality subject years follow-up then the date of last known alive (or date of death) will be used as the censoring date instead.
- For subjects where the date of last follow-up contact across all follow-up visits is missing (i.e. subjects who have not reported a new malignancy and have no Year 2-5 follow-up visits where the new malignancy question was answered as NO), then the study completion or withdrawal date from the Week 52 double-blind treatment period will be used as the censoring date. In calculations, the data for these subjects will be truncated so that subject follow-up years does not exceed 365 days for these subjects.

For subjects who did not enter the follow-up period (i.e. are not in any of the Year 2 to 5 population subsets):

- The study completion or withdrawal date from the Week 52 double-blind treatment period will be used as the censoring date. In calculations, the data for these subjects will be truncated so that subject follow-up years does not exceed 365 days for these subjects. Note: there were four subjects where the study withdrawal or completion date was missing; for these subjects the study agent discontinuation date (IPDISCDT) was used as the last known alive date.

Using this censoring date, the total subject follow-up will be derived for each subject as:

- Subject follow-up (days) = (Censoring Date – Study Treatment Start Date +1)

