5.6.2.10. Follow-Up Adjusted Subject Incidence Rate per 100 Subject Years: Malignancy

New malignancies will be assigned to a timepoint (i.e. Week 52, Year 2, Year 3, Year 4 or Year 5) using the nominal visit where the malignancy was reported. The first timepoint a subject reports a new malignancy will be used in the calculations of follow-up adjusted subject incidence rate per 100 subject years. The cumulative number of subjects with new malignancies to each timepoint will be summarized and follow-up adjusted subject incidence rates calculated.

The follow-up adjusted subject incidence rate presented for each timepoint will be a cumulative follow-up adjusted subject incidence rate from study treatment start date to the appropriate follow-up period. The subject years will be the sum of subject years for all subjects to that timepoint (as described in Section 5.6.2.8).

$$\text{Incidence Rate} = 100 \times \frac{\text{Number of subjects with an event}}{\text{Subject Years}}$$

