5.6.2.11. Follow-Up Adjusted Event Rate per 100 Subject Years: Malignancy

Subjects may report more than one new malignancy.

New malignancies will be assigned to a timepoint (i.e. Week 52, Year 2, Year 3, Year 4 or Year 5) using the nominal visit where the malignancy was reported. All new malignancy events will be included in the calculation of follow-up adjusted event rate per 100 subject years. The cumulative number of new malignancy events to each timepoint will be summarized and follow-up adjusted event rates calculated.

The follow-up adjusted event rate presented for each timepoint will be a cumulative follow-up adjusted event rate from study treatment start date to the appropriate follow-up period. The subject years will be the sum of subject years for all subjects to that timepoint (as described in Section 5.6.2.9).

$$\text{Event Rate} = 100 \times \frac{\text{Number of Events}}{\text{Subject Years}}$$

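### Years 2–5 cumulative mortality and malignancy rates count events by reporting visit but cut person-time by date: a small mismatch, cheap to remove

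*SAP*

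**What the plan says.** The Years 2–5 RAP defines three cumulative rates per 100 subject-years: mortality (5.6.2.7), malignancy subject incidence (5.6.2.10) and malignancy events (5.6.2.11).

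**Numerator.** Deaths are placed in a row "using the survival status nominal visit where the death was reported" and malignancies "using the nominal visit where the malignancy was reported". For the event rate, "All new malignancy events will be included in the calculation of follow-up adjusted event rate per 100 subject years", again by nominal visit. Section 5.6.2.3 rules out dates: "The nominal visit will be used for yearly summaries. There will be no slotting of visits into years using dates".

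**Denominator.** Sections 5.6.2.6, 5.6.2.8 and 5.6.2.9 run each subject's time to the actual event or censoring date and cap it at Day 365, 730, 1095, 1460 or 1825. The cap is there to handle a "date of death or last known alive date which is out of the correct range of study days for a particular year", and a note adds that "individual subjects will only be allowed to contribute a maximum of 365 days for each individual follow-up year". In the event rate, "subject follow-up years will not be truncated at the date of first diagnosis for subjects reporting a new malignancy".

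**Timing.** Contacts in Years 2–5 may fall 30 days either side of the planned day (Years 2–5 RAP 2.3; Protocol 6.4). Section 5.6.2.4 equates Week 52 deaths with those in the Week 52 RAP's on-study period, which runs to Day 372.

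**The concern.** A cumulative rate from treatment start to a timepoint needs events and time from one window. The RAP recognises that dates can fall outside the planned range, but corrects only the denominator. Three mismatches follow.

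- **Late contact.** A death on Day 745, reported at a Year 2 contact on Day 750, counts by Year 2 but brings only 730 days.
- **Early or missed contact.** A death on Day 715, after a Year 2 contact on Day 700, is first reported at Year 3. It is absent from the by-Year-2 count, although in the mortality rate it already stops person-time at Day 715. A first malignancy behaves the same way in the subject-incidence rate. In the event rate only the count is affected.
- **Week 52.** Deaths on Days 366 to 372 count without their time.

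The worked examples in 5.6.2.6 use only in-range dates, so they never show this. For first commercial Benlysta exposure the same RAP assigns years by study day (5.6.2.12) and warns that a subject may be in the numerator but not the denominator (6.2). These rates carry no such warning. They go to health authorities each year (3.1) at two decimals (5.6), and part of each row reflects when sites made contact rather than risk.

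**Working it through.** **Inputs.** A rate of 0.564% and 4,000 subjects (Week 52 RAP 5.1), the ±30-day window, and the caps above. A constant hazard over five years and the contact patterns below are assumptions.

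**The plan's own figure.** 1.96 × √(2 × 0.00564 × 0.99436 / 2,000) = 0.464%, which agrees with the stated ±0.46%. It confirms the inputs and is not in dispute.

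**Late contacts.** Let F(d) = 1 − exp(−0.00564 × d / 365.25). Person-time is the same under either counting rule, so the relative error in the rate is F(365k + 30)/F(365k) − 1. For Week 52 it is F(372)/F(365) − 1. The last column is 1/√(expected deaths).

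| Row | Expected deaths to the cut | Extra deaths, all contacts 30 days late | Relative error | Poisson relative error |
|---|---|---|---|---|
| Week 52 (7 days) | 22.5 | 0.4 | +1.9% | 21% |
| Year 2 | 44.8 | 1.8 | +4.1% | 15% |
| Year 3 | 67.1 | 1.8 | +2.7% | 12% |
| Year 4 | 89.2 | 1.8 | +2.0% | 11% |
| Year 5 | 111.1 | 1.8 | +1.6% | 9.5% |

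At Year 2, 4.1% is 0.023 per 100 subject-years, against a per-arm standard error of 0.119. This is a stress case at the window edge; later contacts would raise it roughly in proportion. For malignancy excluding NMSC, at 0.45 to 0.53 per 100 patient-years (Protocol 1.2), 30/730 of the rate is again about 0.02.

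**Contacts uniform over ±30 days.** The mean late excess is 30/4 = 7.5 days. In the newest row an early contact also ends a survivor's person-time, so nothing offsets that excess: 7.5/730 = 1.0% at Year 2, 7.5/1095 = 0.7% at Year 3, 7.5/1460 = 0.5% at Year 4. Once a later contact is in the data, early contacts lose 7.5 days' worth of events and the net is about 0%. Year 5 never has a later contact, so 7.5/1825 = +0.4% remains.

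**Missed contacts, recovered at a later visit.** Suppose a share p of Year 3 and Year 4 contacts is missed. The documents give no value for p.

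- Year 3 row: −365p/1095 = −3.3% at p = 10% and −6.7% at 20%.
- Year 4 row: −(365p + 365p²)/1460 = −2.75% and −6.0%.

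These losses appear only in back rows of later reports. If misses come only from the pandemic, fewer subjects are exposed. At least 2,000 had completed Week 52 before an interim report submitted in December 2016 (Week 52 RAP 4.1). Their Year 3 and Year 4 contacts were due by December 2018 and December 2019. Assuming those contacts escaped, both figures are at most about half: −1.7% (−3.3%) at Year 3 and about −1.4% (−3.0%) at Year 4.

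**Partial dates.** Section 5.6.1.1 imputes 1 January for a year-only date and the 1st for a missing day. Assume events uniform within the study year and anniversaries uniform over the calendar year. Then 1 January falls before the anniversary in 1/2 of cases, and the 1st of the month in 1/24 (4.2%). Flooring at the last earlier contact does not cure this: with contacts uniform over ±30 days, half precede the anniversary, so 1/2 × 1/2 = 25% of year-only dates would still move to an earlier row.

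**The case against.** The strongest reply is that nothing inferential rests on this. Years 2–5 have no hypotheses (2.4), no testing (5.5), and no planned between-arm difference or interval (7.1, 7.2). The larger figures are stress cases or assumed miss rates. Nominal-visit counting also has merits: cumulative counts equal the running sum of the yearly tables, Week 52 agrees with a reported analysis, and no event depends on an imputed date. All of this stands. It makes the point minor, and it means a date-based count needs its own partial-date rule. It does not pair the numerator with its denominator.

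A reader might infer more, in three ways that the documents do not support.

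- **That the arm comparison is biased.** Both arms follow one rule, and nothing shows that contact timing or missed contacts differ by arm.
- **That the pandemic makes the error large.** Section 2.3 says only that more contacts may be missed or out of window, after all subjects had completed Year 2. It also expects some data to be filled in later. An event entered late on its own nominal form causes no error from a missed contact.
- **That the by-Year-3 COVID-19 row is badly understated.** Its relative loss would simply equal whatever miss rate is assumed among the subjects exposed, applied to an unknown and possibly very small count.

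**Conclusion.** Minor, but wrong as written. All three cumulative rates pair events from one window with person-time from another. Within the contact window the distortion is at most about 4% at Year 2 and less later. With evenly spread contacts it is 1% or less in Years 2–5. Under the assumed missed contacts it reaches 6.7% in one back row, or about half that if misses are purely pandemic-related. Every figure is below the Poisson error on the same deaths. The direction can go either way in back rows for Years 2–4, but at Year 5 it can only be upward. These sizes rest on a constant hazard of 0.564 per 100 subject-years and on assumed contact patterns. The mismatch itself rests only on the text.

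**What to change.** For the cumulative rates only (5.6.2.7, 5.6.2.10, 5.6.2.11; Tables 3.6–3.8 and 3.14):

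- Count an event by Year k if its date is on or before the Day 365k cut used for person-time. Dates of death and diagnosis are already collected or derived (5.6.2.4, 5.6.2.5).
- For Week 52, use one limit for both parts. Either count to Day 365, or cut person-time at Day 372 to stay in line with the Week 52 report.
- Show events after Day 1825 as a separate count.
- Where a partial death or diagnosis date does not settle the row, keep the event in its nominal-visit row. Within the recorded month or year, set its imputed date no earlier than the later of two dates: the first day of that row, and the last contact at which the subject was alive (deaths) or answered NO (malignancy). Section 5.6.1.1 now gives deaths a last-known-alive floor and diagnoses none. For malignancy, this date affects person-time only in the subject-incidence rate.
- Leave the yearly and SOC/PT tables on nominal visit, with a footnote that cumulative counts may not equal their running sum.

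The cost is minor reprogramming of four tables and a slight restatement of the Year 2 rates, which 3.1 already allows for since data may change until the final analysis. Cumulative counts may then differ from the nominal-visit tables and, if Day 365 is chosen, from the Week 52 report.

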5.6.2.8. Subject Years Follow-Up: Malignancy Subject Incidence Rate

In order to calculate the follow-up adjusted subject incidence rate of new malignancies per 100 subject years by follow-up year (cumulative), the subject years follow up will need to be defined for each subject at each follow-up time point.

This will be done in a similar way to subject years follow-up for mortality (Section 5.6.2.6) but will use date of follow-up contact, rather than date last known alive, as the censoring date. And will use date of diagnosis, rather than date of death as the event date (note: date of diagnosis using SDTM.CE.CESTDTC).

Note: New malignancies reported at Week 52 with a diagnosis of 'UNKNOWN,NO FOLLOW-UP' (SDTM.CE.CETERM) will not be considered to be malignancies (see Section 5.6.2.5).

For each subject a single date of first new malignancy or last follow-up contact date will be derived as follows.

For subjects who entered the follow-up period (i.e. are in any of the Year 2 to 5 population subsets):

- For subjects who have a new malignancy reported, the date of diagnosis of the first new malignancy will be used in the subject follow-up years calculations. Note: this includes malignancies reported by Week 52.
- For subjects who have not reported a new malignancy at any follow-up visit, the date of last follow-up contact across all follow-up visits will be found (using all visits where the new malignancy question was answered as NO) and used as the censoring date. If this follow-up contact date is later than the last known alive date (or date of death) used in the mortality subject years follow-up then the date of last known alive (or date of death) will be used as the censoring date instead.
- For subjects where the date of last follow-up contact across all follow-up visits is missing (i.e. subjects who have not reported a new malignancy and have no Year 2-5 follow-up visits where the new malignancy question was answered as NO), then the study completion or withdrawal date from the Week 52 double-blind treatment period will be used as the censoring date. In calculations, the data for these subjects will be truncated so that subject follow-up years does not exceed 365 days for these subjects.

For subjects who did not enter the follow-up period (i.e. are not in any of the Year 2 to 5 population subsets):

- For subjects who have a new malignancy reported, the date of diagnosis of the first new malignancy will be used in the subject follow-up years calculations.
- If a subject did not have a new malignancy reported by Week 52, the study completion or withdrawal date from the Week 52 double-blind treatment period will be used as the censoring date. In calculations, the data for these subjects will be truncated so that subject follow-up years does not exceed

365 days for these subjects. Note: there were four subjects where the study withdrawal or completion date was missing; for these subjects the study agent discontinuation date (IPDISCDT) was used as the last known alive date.

Using this date of malignancy diagnosis or censoring date, the total subject follow-up will be derived for each subject as:

- Subject follow-up (days) = (Date of malignancy diagnosis/Censoring Date – Study Treatment Start Date +1)

The amount of subject follow-up contributing to each of the cumulative timepoints (by Week 52, by Year 2 follow-up, by Year 3 follow-up, by Year 4 follow-up, by Year 5 follow-up) is described below. In order to account for date of diagnosis or censoring date which is out of the correct range of study days for a particular year, the following derivation will be used:

Study Year	Subject Follow-Up (days)
By Week 52	Minimum (Date of diagnosis/Censoring Date – Treatment Start Date + 1, 365)
By Year 2 Follow-Up	Minimum (Date of diagnosis/Censoring Date – Treatment Start Date + 1, 730)
By Year 3 Follow-Up	Minimum (Date of diagnosis/Censoring Date – Treatment Start Date + 1, 1095)
By Year 4 Follow-Up	Minimum (Date of diagnosis/Censoring Date – Treatment Start Date + 1, 1460)
By Year 5 Follow-Up	Minimum (Date of diagnosis/Censoring Date – Treatment Start Date + 1, 1825)

Note: individual subjects will only be allowed to contribute a maximum of 365 days for each individual follow-up year, regardless of when the follow-up visit was performed.

Note: For each subject, subject follow-up for each time period is cumulative since study treatment start date. For example, 'by Year 2 follow-up' includes follow-up time during Year 1 and follow-up time during Year 2 (to a maximum of 730 days).

The subject follow-up days will be converted to years as follows:

- Subject follow-up (years) = subject follow-up (days) / 365.25

The total follow-up years will be calculated for each of the timepoints as the sum of the subject follow-up years for that timepoint for all subjects in the As-Treated population.

